## **7.6 Post-study Follow-up**

Once patients have progressed, they will be followed via phone call (or access via available medical records) every 3 months after disease progression for overall survival. Medical records including laboratory, pathology, operative, and radiology reports will be obtained at the discretion of the principal investigator with permission from the patient. Patients who have stopped the study drug due to toxicity should be followed until resolution of toxicity or the safety follow-up visit, whichever comes later.

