## **7.2 Day 1 Visit Assessments (All cycles)**

Patients will make clinic visits for tests and observations according to the schedule in Schedule of Study Assessments (Appendix 1). Assessments may be performed up to 2 days and CT/ scans may be performed up to 7 days prior to the scheduled study visit day. The results of study blood tests must be available and reviewed by study site staff for toxicity and adverse events before the next dose of entinostat is administered. Obtaining blood for these tests may be performed locally or drawn by a home health care worker if clinic visits are not practical. Results must be sent to the investigator. Other observations should be performed prior to the next dose of entinostat.

Required procedures are as follows:

- Concomitant medications
- Adverse Events
- Hematology (as at screening)
- Blood chemistries (as at screening with the exception of magnesium which does not need to be done unless clinically indicated)
- Symptom directed PE (capture B symptoms)
- Vital signs and weight
- ECOG performance score
- Clinical disease assessment for palpable or visual lesions
- CT scan for disease assessment (up to 7 days prior to day 1 of odd cycles beginning with Cycle 3). In patients completing >9 cycles, scans are required every 3-4 months and/or omitting the use of contrast dye to every other restaging. Follow-up scans should include

the area of interest, the prospectively selected indicator lesion(s); the same method used at baseline should be used for all serial measurements.

- Entinostat compliance assessment

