### **7.4 End of Treatment Visit Assessments**

This visit should occur within one week from the date that the physician decides to discontinue study treatment. If the physician decides to discontinue study treatment due to disease progression, this visit should be completed before beginning the patient on another therapy.

Required procedures are as follows:

- Physical examination
- Vital signs and weight
- ECOG performance score
- ECG (as at screening)
- Concomitant medications
- Adverse events
- Hematology (as at screening )
- Blood chemistries (as at screening with the exception of magnesium which does not need to be done unless clinically indicated)
- Contrast CT scans for disease assessment if progression has not been observed previously. Follow-up scans should include the area of interest, the prospectively selected indicator lesion(s); the same method used at baseline should be used for all serial measurements. Octreotide scans should be done if any mass detected by CT completely resolves during treatment.
- Compliance assessment
- Clinical disease assessment for palpable or visual lesions

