## **9. REMOVAL OF PATIENTS**

Patients have the right to withdraw from the study at any time and for any reason without prejudice to their future medical care by the physician or the institution. If a patient chooses to withdraw from study treatment, they will be asked to continue to receive follow-up via telephone. Patients have the right to withdraw completely or continue to be followed long term with telephone calls.

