#### *Secondary Efficacy*

- Duration of response for patients who achieve CR or PR
- Duration of overall survival
- Duration of progression-free survival

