## APPENDIX 1: SCHEDULE OF STUDY ASSESSMENTS

Assessments	Screening	Cycle 1				Even Cycles (2,4,6, etc.)		Odd Cycles (3,5,7, etc)		EOT	Safety F/up
		D 1 +/- 3 days	D 8 +/- 3 days	D 15 +/- 3 days	D22 +/- 3 days	D1 +/- 3 days	D15  +/- 3 days	D1 +/- 3 days	D15  +/- 3 days		
Informed consent	X										
Medical History & Medications	X 										
Physical exam, vitals, weight, Performance status (ECOG)	X	X 	X 	X 	X 	X 	X 	X 	X 	X	X
Hematology and Blood chemistry tests	X 	X 		X 		X 	X 	X 	X 	X 	X
Urinalysis	X									X	
Thyroid functions: TSH, T3, T4	X									X	
Serum pregnancy test (WOCBP only)	X										
12-lead ECG	X									X	X 
Disease assessment / contrast CT and octreotide scan	X 							X 		X 	
Clinical Disease Assessment	X	X	X	X		X	X	X	X	X	
Tumor Biopsy (if archival tissue not available)	X										
Adverse events / concomitant medication information collection		X	X	X	X	X	X	X	X	X	X
Entinostat compliance assessment		X	X	X	X	X	X	X	X	X	
Entinostat drug administration		X	X	X	X	X	X	X	X		
Long Term Telephone Contact 											

Note all medications taken within 28 days of C1D1

Only a symptom directed physical exam is required at these visits.

Hematology: CBC with differential, platelets, RBC, HGB, HCT; Blood chemistry: ALT, AST, alkaline phosphatase, albumin, total bilirubin, BUN, calcium, creatinine, electrolytes (sodium, potassium, magnesium {only at screening unless clinically indicated}, chloride, bicarbonate), glucose, LDH, phosphorus, total protein, uric acid.

performed only if one was not done within 28 days prior to C1D1; Octreotide scan required only at screening.

Follow-up scans must include the area of interest, the prospectively selected indicator lesion(s); the same method used at baseline should be used for all serial measurements. Required every 3 cycles.

Performed only if disease progression was not previously documented

ECG required if new abnormality is observed during study and not resolved at EOT.

Following patient termination from study, every 2 months until disease progression and every 3 months after disease progression for overall survival

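### Section 7.6 starts survival contact only after progression, contrary to Appendix 1, and no scan is scheduled after the end-of-treatment CT for patients who stop entinostat progression-free

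*Combined protocol and SAP*

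**What the plan says.** Four places govern contact after treatment.

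- Section 7.6 makes progression the starting point of survival contact: "Once patients have progressed, they will be followed via phone call (or access via available medical records) every 3 months after disease progression".
- The same section adds: "Patients who have stopped the study drug due to toxicity should be followed until resolution of toxicity or the safety follow-up visit, whichever comes later".
- Footnote 8 of Appendix 1, attached to the long-term telephone row, reads: "Following patient termination from study, every 2 months until disease progression and every 3 months after disease progression for overall survival".
- Section 9 says: "If a patient chooses to withdraw from study treatment, they will be asked to continue to receive follow-up via telephone".

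On imaging, scans during treatment are set by section 7.2: "CT scan for disease assessment (up to 7 days prior to day 1 of odd cycles beginning with Cycle 3". At the end-of-treatment visit section 7.4 requires: "Contrast CT scans for disease assessment if progression has not been observed previously". Footnote 6 of Appendix 1 agrees. No scan is listed at the safety visit (7.5), in 7.6, or in the safety follow-up column of Appendix 1. What remains is record retrieval: "Medical records including laboratory, pathology, operative, and radiology reports will be obtained at the discretion of the principal investigator", with the patient's permission.

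The secondary efficacy endpoints in section 11.2 are "Duration of response for patients who achieve CR or PR", overall survival and progression-free survival. Section 11.5 defines analysis populations but gives no event definition, censoring rule or method for any of the three.

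**The concern.** The patients at issue stop entinostat before progression. They are foreseeable: Tables 6-1 and 6-2 require permanent discontinuation after a hold of 4 consecutive weeks, after certain toxicities at 2 mg, or when more than half the doses are missed in a 6-week period.

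Two things could go wrong for them. First, sites have two different instructions on whether to contact them before progression. With up to four centers, practice may differ, and survival status could be missing for some patients because of which paragraph the site followed. Second, once the drug stops there is no planned way to find RECIST progression. A telephone call can establish death but not radiographic progression. Their PFS and duration of response would then end at the last scan, or at a date learned by telephone, and nothing says which. Censoring when a patient stops for toxicity may not be independent of prognosis.

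**Working it through.** **1. Contact rules side by side.**

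| Place | Patients covered | Start | Interval |
|---|---|---|---|
| 7.6, opening sentence | those who have progressed | progression | 3 months |
| 7.6, toxicity sentence | those stopping for toxicity | drug stop | none given; ends at resolution or safety visit, the later |
| Section 9 | those who choose to withdraw from treatment | not tied to progression | none given |
| Appendix 1, footnote 8 | all, after termination | termination | 2 months before progression, 3 months after |

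The first and last rows cannot both describe a patient who stops progression-free. Section 9 leans toward footnote 8 but does not clearly cover a protocol-required discontinuation.

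**2. Last planned contact if 7.6 is read alone.** The end-of-treatment visit falls within one week of the decision to stop (7.4), and the safety visit within 30 days after that (7.5). So the last planned contact is at most 7 + 30 = 37 days after the decision, unless a toxicity is still unresolved. Under 7.6 the calls restart only at progression, and no scheduled assessment would detect progression. Under footnote 8 contact continues whether or not progression is recorded.

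**3. Imaging.** On treatment, section 7.2 places scans before odd cycles from cycle 3. Until cycle 9, successive scans are therefore about 2 × 28 = 56 days apart, and a progression date falls within a known interval. (Footnote 5 of Appendix 1 says every 3 cycles, 3 × 28 = 84 days. That mismatch also needs reconciling but does not change this point.) After drug stop there is one CT, at the end-of-treatment visit, and then no scheduled interval at all.

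**4. How many patients.** The documents give no rate of stopping without progression. Taking 15% to 30% purely as an assumption:

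- of 23 response-evaluable patients: 0.15 × 23 = 3.5 to 0.30 × 23 = 6.9;
- of 32 response-evaluable patients: 0.15 × 32 = 4.8 to 0.30 × 32 = 9.6;
- responders at the targeted 35%: 0.35 × 23 = 8.05, of whom 0.15 × 8.05 = 1.2 to 0.30 × 8.05 = 2.4.

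Two cautions apply. Response-evaluable patients have already completed two cycles and had the cycle 3 CT (11.5), so those who stop earlier for toxicity are outside these counts. And nothing shows that responders stop at the same rate as other patients.

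**5. Primary endpoint.** Section 11.2 takes best response during administration of the drug, so follow-up after treatment does not enter. The plan's design figures reproduce. With 9 patients at a 15% response rate, P(0 or 1 response) = 0.85^9 + 9 × 0.15 × 0.85^8 = 0.2316 + 0.3679 = 0.5995, against the stated 60%. Expected size = 9 + (1 − 0.5995) × 14 = 14.61, as stated. With 6 or more of 23 required, exact type I error is 0.099 and power 0.804. None of these depends on the point raised here. The plan states no event count or power for the three secondary endpoints, so there is no planned figure to recompute for them.

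**The case against.** A reader might infer that these patients get no further scans and that duration of response, PFS and OS cannot be measured for them. The documents do not support that.

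- A CT is required at end of treatment when progression has not been seen, so PFS and duration of response are observed up to that scan and can be censored there.
- Footnote 8 plans contact before progression and section 9 asks for it after withdrawal. Vital status can be learned by telephone, so OS is measurable wherever those two provisions are followed.
- The toxicity sentence in 7.6 can be read as adverse-event follow-up, in line with section 6.2, and not as an end to survival follow-up.
- The sentence on medical records is not expressly limited to patients who have progressed, so radiology reports may be obtained.

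A reader might also divide the prevalence of 35 by the incidence of 5 per 100,000 in section 2.1.1, get 7 years of disease, and infer that most follow-up falls after drug stop. That fails: the same section reports incidence rising from one to five, so the steady state behind the ratio is absent. The figures also cover all neuroendocrine tumours, not relapsed or refractory stage IV disease, and say nothing about time on drug.

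These arguments remove the claim that measurement is impossible. They leave three facts: 7.6 and footnote 8 disagree, no scan is scheduled after the end-of-treatment CT, and no rule says how such patients enter PFS or duration of response. Permission to collect reports at discretion is not a systematic collection.

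**Conclusion.** The point holds as a conflict over survival contact together with a gap in progression data. A site following 7.6 as worded could lose OS follow-up on patients who stop progression-free; a site following footnote 8 would not. For PFS and duration of response the gap exists under either text, because neither schedules imaging after the end-of-treatment CT.

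The effect is confined to three secondary endpoints; the response rate and both Simon decisions stand. On the assumed 15% to 30%, about 3 to 7 of 23 patients would be affected and, if responders stop at the same rate, 1 or 2 of about 8 responders. The size and direction of any bias from censoring cannot be derived from the documents. This is a cheap improvement, best made before patients stop treatment, since uncollected follow-up may be hard to recover later.

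**What to change.** - **Section 7.6:** reconcile it with footnote 8 so that every patient, progressed or not, is contacted from end of treatment on the footnote 8 schedule. State that the toxicity sentence concerns adverse-event follow-up and does not end survival contact, and keep sections 6.2 and 9 consistent with this.
- **Scans after stopping without progression:** make retrieval of routine-care scan reports and images systematic, with patient permission, until RECIST progression, death or new anticancer therapy. Date progression from scans, not from telephone report.
- **Section 11.5:** define events and censoring for PFS and duration of response to match, including how new anticancer therapy and a missing later scan are handled.

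The cost is wording in 7.6 and footnote 8, a short addition to 11.5, and record retrieval at up to four centers. The calls are already in Appendix 1 and record access is already in 7.6. Routine-care scans will come at irregular intervals, so progression dates will be less precise than on treatment, and a patient with no routine scan would still be censored at the last CT.

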## **8. CORRELATIVE STUDIES**

### **Biomarker Evaluations**

#### **8.1 Tissue Sampling**

A requirement of phase 2 protocol entry is the presence of a metastatic focus accessible to biopsy. All patients who enter the second phase of the trial that would require a specific gene expression profile for eligibility will be asked to undergo a single image-guided fine-needle biopsy. For patients in the first part of the protocol who agree, a minimum of 0.05mg of fresh metastatic tissue (a single needle core biopsy) will be obtained prior to treatment initiation for RNAseq and master regulator analysis. If the protocol extends to the second part, all patients

will be required to undergo biopsy in order to establish eligibility for the second part of the study if it is initiated.

## **9. REMOVAL OF PATIENTS**

Patients have the right to withdraw from the study at any time and for any reason without prejudice to their future medical care by the physician or the institution. If a patient chooses to withdraw from study treatment, they will be asked to continue to receive follow-up via telephone. Patients have the right to withdraw completely or continue to be followed long term with telephone calls.

## **10. ADVERSE EVENTS: LIST AND REPORTING REQUIREMENTS**

### **10.1 Adverse events**

Investigational Agent: Include a comprehensive list of all reported adverse events and any potential risks (such as the toxicities seen with another agent of the same class or risks seen in animals administered this agent) as provided by the manufacturer.

Adverse Event List(s) for Other Agent(s): For each commercial agent, please provide a list of those adverse events most likely to occur on this study, and refer the reader to the package insert(s) for the comprehensive list of adverse events.

### **10.2 Definitions**

#### **Adverse Event:**

An adverse event (AE) is any untoward or unfavorable medical occurrence in a human subject, including abnormal sign, symptom or disease, temporally associated with the subject's participation in research, whether or not considered related to the subject's participation in the research. Abnormal results of diagnostic procedures are considered to be adverse events if the abnormality:

- results in study withdrawal
- is associated with a serious adverse event
- is associated with clinical signs or symptoms
- leads to additional treatment or to further diagnostic tests
- is considered by the investigator to be of clinical significance

**Serious Adverse Event:**

Adverse events are classified as serious or non-serious. A serious adverse event is any AE that is:

- fatal
- life-threatening
- requires inpatient hospitalization/prolongation of existing hospitalation, unless:
  - routine treatment or monitoring of the studied indication, not associated with any deterioration in condition (procedures such as central line placements, paracentesis, pain control)
  - elective or pre-planned treatment for a pre-existing condition that is unrelated to the indication under study and has not worsened since the start of study drug
  - treatment on an emergency outpatient basis for an event not fulfilling any of the definitions of an SAE given above/below and not resulting in hospital administrations
  - social reasons and respite care in the absence of any deterioration in the patient's general condition
- results in persistent or significant disability or incapacity
- a congenital anomaly or birth defect
- an important medical event

Important medical events are those that may not be immediately life threatening, but are clearly of major clinical significance. They may jeopardize the subject, and may require intervention to prevent one of the other serious outcomes noted above. For example, drug overdose or abuse, a seizure that did not result in in-patient hospitalization or intensive treatment of bronchospasm in an emergency department would typically be considered serious.

All adverse events that do not meet any of the criteria for serious events should be regarded as non-serious adverse events.

**Unanticipated Problem:**

An unanticipated problem is any incident, experience or outcome involving risks to subjects or others in any human subjects research that meets all of the following criteria:

- Unexpected (in terms of nature, severity or frequency) given (a) the research procedures that are described in the IRB-approval protocol and informed consent document, and (b) the characteristics of the subject population being studied;
- Related or possibly related to participation in such research (e.g., there is a reasonable possibility that the incident, experience or outcome may have been caused by the procedures involved in such research); and
- Suggests that the research places subjects or others at a greater risk of harm (including physical, psychological, economic or social harm) than was previously known or recognized.

### **Adverse Event Reporting Period**

The study period during which adverse events must be reported is normally defined as the period from the initiation of any study procedures (e.g., after the first dose of study treatment) to the end of the study treatment (e.g., last dose of study treatment) and/or follow-up. For this study, the study treatment follow-up is defined as 30 days following the last administration of study treatment, **or 30 days following the decision to remove the subject from study treatment, whichever is earliest.**

### **Baseline/Preexisting Condition**

A baseline/preexisting condition is one that is present at the start of the study. A preexisting condition should be recorded as an adverse event if the frequency, intensity, or if the character of the condition worsens during the study period.

### **General Physical Examination Findings**

At screening, any clinically significant abnormality should be recorded as a preexisting condition. At the end of the study, any new clinically significant findings/abnormalities that meet the definition of an adverse event must also be recorded and documented as an adverse event.

### **Post-study Adverse Event**

All unresolved adverse events should be followed by the investigator until the events are resolved, the subject is lost to follow-up, or the adverse event is otherwise explained. At the last scheduled visit, the investigator should instruct each subject to report any subsequent event(s) that the subject, or the subject's personal physician, believes might reasonably be related to participation in this study.

### **Abnormal Laboratory Values**

A clinical laboratory abnormality should be documented as an adverse event if any one of the following conditions is met:

- The laboratory abnormality is not otherwise refuted by a repeat test to confirm the abnormality
- The abnormality suggests a disease and/or organ toxicity
- The abnormality is of a degree that requires active management (e.g., change of dose, discontinuation of the drug, more frequent follow-up assessments, further diagnostic investigation, etc.).

### **Hospitalization, Prolonged Hospitalization or Surgery**

Any adverse event that results in hospitalization or prolonged hospitalization should be documented and reported as a serious adverse event unless specifically instructed otherwise in

this protocol. Any condition responsible for surgery should be documented as an adverse event if the condition meets the criteria for an adverse event.

Neither the condition, hospitalization, prolonged hospitalization, nor surgery are reported as an adverse event in the following circumstances:

- Hospitalization or prolonged hospitalization for diagnostic or elective surgical procedures for a preexisting condition. Surgery should **not** be reported as an outcome of an adverse event if the purpose of the surgery was elective or diagnostic and the outcome was uneventful.
- Hospitalization or prolonged hospitalization required to allow efficacy measurement for the study.
- Hospitalization or prolonged hospitalization for therapy of the target disease of the study, unless it is a worsening or increase in frequency of hospital admissions as judged by the clinical investigator.

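### Section 10.2 gives conflicting reporting rules for an elective surgical admission when a preexisting condition has worsened on study

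*Combined protocol and SAP*

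**What the plan says.** Three subsections of section 10.2 (Definitions) bear on the same admission.

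- **Serious Adverse Event.** An AE is serious if it "requires inpatient hospitalization/prolongation of existing hospitalation, unless" one of the listed exemptions applies. One exemption is for "elective or pre-planned treatment for a pre-existing condition that is unrelated to the indication under study and has not worsened" since study drug was started. Another covers "routine treatment or monitoring of the studied indication, not associated with any deterioration in condition".
- **Baseline/Preexisting Condition.** "A preexisting condition should be recorded as an adverse event if the frequency, intensity, or if the character of the condition worsens during the study".
- **Hospitalization, Prolonged Hospitalization or Surgery.** The default is that an AE leading to admission "should be documented and reported as a serious adverse event unless specifically instructed otherwise in" the protocol. A list of exceptions follows, introduced by: "Neither the condition, hospitalization, prolonged hospitalization, nor surgery are reported as an adverse event in the following circumstances". Its first bullet reads "Hospitalization or prolonged hospitalization for diagnostic or elective surgical procedures for a preexisting condition". Its third bullet, on therapy of the target disease, does withhold the exemption when there is a worsening or more frequent admissions.

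The safety endpoint in section 11.2 is the incidence, severity and duration of AEs, including SAEs. Section 11.4 bases the continuing safety assessment on AEs, SAEs and discontinuations due to AEs, and sets no formal stopping rule for safety. Section 10.4.4 requires SAEs that are not unanticipated problems to reach the data and safety monitoring committee within 24 hours. Appendix 5, section 10, sets the same limit for affiliate sites reporting SAEs to the overall principal investigator.

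**The concern.** The SAE exemption carries two limits: the condition must be one "that is unrelated to the indication under study and has not worsened since the start of study drug". The first bullet of the hospitalization list carries neither. It also reaches further, because it takes the condition itself out of AE reporting and does not merely affect the seriousness grading of the admission.

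The limit that matters most is worsening. A preexisting condition that deteriorates after dosing begins is the kind of event a safety endpoint is meant to capture. If it leads to an operation that is still classed as elective, two subsections point to an AE and an SAE, and a third says that nothing is reported. The error can run in only one direction, because the bullet can remove events but cannot add them. With a small single-arm trial and no formal stopping rule, the safety review depends on complete counts. An event that is never classed as an SAE also never starts the 24-hour reporting clock.

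**Working it through.** The plan states no figure to reproduce, so the check is a comparison of the rules for four kinds of elective surgical admission for a preexisting condition.

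| Case | Baseline rule and SAE definition | First bullet of the hospitalization list | Result |
|---|---|---|---|
| 1. Unrelated to tumor, not worsened | Not an AE under the baseline rule; the admission also meets the SAE exemption | Not reported | Agree |
| 2. Unrelated to tumor, worsened | AE under the baseline rule; the SAE exemption fails on worsening, so SAE | Not reported; the condition itself is also excluded | Direct conflict |
| 3. Tumor-related, worsened | AE; outside the elective exemption, and the routine-treatment exemption fails on deterioration, so SAE | Not reported if read as elective surgery for a preexisting condition; but the third bullet withholds the exemption if the admission counts as therapy of the target disease | Arguable; depends on which bullet applies |
| 4. Tumor-related, not worsened | Not an AE under the baseline rule, so it cannot be an SAE; the routine-treatment exemption may apply as well | Not reported | Conflict at most arguable |

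Case 2 is decisive. The next question is whether any text settles it.

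- *Precedence.* Nothing in section 10.2 says which subsection governs. The default rule in the hospitalization subsection yields to specific instructions elsewhere in the protocol, but the two exemption lists are themselves the instructions that disagree.
- *Deliberate design.* The third bullet of the same list has a worsening limit and the first has none. The omission is therefore not a general drafting convention of that list.

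**Size.** The documents give no rate of elective admission, of worsening, or of the two together, so no expected number of affected patients can be derived. What can be given is the effect of one patient on the proportion with at least one SAE, assuming that patient has no other SAE:

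- Formula: shift = 1/n, where n is the number in the safety population. Section 11.5 defines this as everyone who receives at least one dose.
- Upper limit on n: 40, the maximum enrollment in section 3.3. Section 11.5 counts a patient as enrolled at consent, so the number dosed may be lower.
- At n = 40: 1/40 = 2.5 percentage points. This is the smallest shift that one such patient can cause.
- If only 32 were dosed (illustration only): 1/32 = 3.1 points.

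If no such admission occurs, the shift is zero.

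**The case against.** The best counter-argument comes from the same subsection. Just before its list, it says that a condition responsible for surgery is documented as an AE when it meets the AE criteria. A worsened preexisting condition meets them under the baseline rule, and section 10.3 requires every AE in the study period to be recorded. On that reading the event is captured after all. This has weight, and it shows that recording the condition is a defensible reading. It does not settle the matter, because the list that follows names the condition itself among the things not reported. The subsection is then in tension with itself as well as with the SAE definition.

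A reader might also infer three stronger points, which the documents do not support.

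- *That the same contradiction holds for tumor-related elective surgery.* An unworsened tumor condition is not an AE under the baseline rule and may fall under the routine-treatment exemption. A worsened one is at least partly caught by the third bullet of the hospitalization list.
- *That several percentage points of SAEs are at stake.* This would need an admission rate that the documents do not give. It would also be a mistake to divide by 32 or 23 as if they were the safety population: those are targets for response-evaluable patients.
- *That the bias differs by site.* Up to four centers could read the text differently, but nothing shows that they would. Appendix 5, section 7, has a compliance coordinator verify that toxicities and SAEs at affiliate sites have been reported. That check does not repair the wording, but it means that site variation is a possibility and not a finding.

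**Conclusion.** Wrong as written, with low severity. For a preexisting condition unrelated to the tumor that worsens on study and leads to an elective surgical admission, section 10.2 gives an AE and an SAE under two subsections and no report under a third, with no order of precedence. For tumor-related conditions the conflict is at most arguable.

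The consequence is possible under-counting in a secondary safety endpoint and in the inputs to the ongoing safety review, and a missed 24-hour report. The total effect cannot be estimated from the documents. Per affected patient it is at least 2.5 points on the SAE proportion, given no more than 40 dosed and no other SAE in that patient. The scenario needs a preexisting condition, on-study worsening and an admission still classed as elective, all in one patient, so it may be rare or absent. The primary response endpoint, the sample size and the stage 1 decision rule are not affected.

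**What to change.** In section 10.2, under Hospitalization, Prolonged Hospitalization or Surgery:

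1. Restrict the first bullet to a preexisting condition that has not become worse since study drug was started.
2. Add a sentence saying that a preexisting condition that worsens is recorded as an AE under the Baseline/Preexisting Condition rule, and that any resulting hospitalization is then assessed under the Serious Adverse Event definition.

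Do not also carry over the requirement that the condition be unrelated to the studied indication. The bullet covers diagnostic as well as elective procedures, so that limit would take tumor-related diagnostic admissions without deterioration out of this exemption, whereas the SAE definition exempts routine monitoring of the tumor. It would replace one mismatch with another.

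The cost is one added qualifier and one sentence in the protocol, and possibly a few more AE and SAE reports.
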